### 5.1 Clinical variables of interest for the study

The only source for clinical information will be administrative databases in all its parts.

[figure not shown]
We will focus primarily on the following set of clinical data:

- Biopsy at diagnosis;
- Presence of metastatic NSCLC at diagnosis;
- Neoadjuvant treatment before lung cancer surgical resection;
- Lung cancer main surgical resection;
- Length of stay in hospital after lung major surgery;
- Main information regarding anti-cancer drug treatments at the first diagnosis and for subsequent lines
- Multidisciplinary team (MDT) meeting discussion;
- Radiotherapy (RT) in the end of life;
- Death;
- Integrated home care utilization;
- Hospice care utilization.

[figure not shown]

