### 5.2 Key performance indicators for monitoring care pathway in NSCLC patients

The following key performance indicators (KPIs) will be measured to investigate the appropriateness of NSCLC patient care pathways, with a special focus on the use of immunotherapy.

[figure not shown]
BOZZA - KPI -	
1	
Percentage of patients who performed biopsy within 7 days from the date of examination prescription
 
NUM: Number of patients who performed biopsy within 7 days from prescription; DEN: Total number of patients identified by the algorithm who performed biopsy;

2	
Percentage of mNSCLC patients at diagnosis
 
NUM: Number of patients with metastases (presence of one of the following codes (197*,198*,199*) in all position of diagnosis codes for index hospitalization); DEN: Total number of patients identified by the algorithm;

3	
Percentage of major surgical resections within the year of analysis.
 
NUM: Number of patients who underwent to lung cancer major surgical resection; DEN: Total number of patients identified by the algorithm;

	
To identify major surgical procedures for lung, the following codes of ICD-9-CM classification will be identified:
 
  
 ICD-9-CM coding related to major surgery on lung	
   
 32.01	ENDOSCOPIC EXCISION OR DESTRUCTION OF LESION OR TISSUE OF BRONCHUS	
 
 32.29	OTHER LOCAL EXCISION OR DESTRUCTION OF LESION OR TISSUE OF LUNG	
 
 32.3	SEGMENTAL RESECTION OF LUNG	
 
 32.4	LOBECTOMY OF LUNG	
 
 32.5	COMPLETE PNEUMONECTOMY	
 
 34.6	SCARIFICATION OF PLEURA	
  
	ICD-9-CM coding related to major surgery on lung		32.01	ENDOSCOPIC EXCISION OR DESTRUCTION OF LESION OR TISSUE OF BRONCHUS	32.29	OTHER LOCAL EXCISION OR DESTRUCTION OF LESION OR TISSUE OF LUNG	32.3	SEGMENTAL RESECTION OF LUNG	32.4	LOBECTOMY OF LUNG	32.5	COMPLETE PNEUMONECTOMY	34.6	SCARIFICATION OF PLEURA
ICD-9-CM coding related to major surgery on lung															
32.01	ENDOSCOPIC EXCISION OR DESTRUCTION OF LESION OR TISSUE OF BRONCHUS														
32.29	OTHER LOCAL EXCISION OR DESTRUCTION OF LESION OR TISSUE OF LUNG														
32.3	SEGMENTAL RESECTION OF LUNG														
32.4	LOBECTOMY OF LUNG														
32.5	COMPLETE PNEUMONECTOMY														

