34.6	SCARIFICATION OF PLEURA														
4	
Percentage of surgical patients on the total number of patients with exploratory thoracotomy in inpatient setting.            NUM: Total of patients with only exploratory thoracotomy procedure (Cod 34.02);            DEN: Number of surgical patients;            For major surgery, ICD-9-CM codes were selected as reported for KPI 3.            Surgical patients defined as patients who receive any surgical procedure (major and/or explorative)
														
5	
Percentage of patients undergoing neoadjuvant therapy ( CT or CT+RT within 6 months prior to the first major resection date)            NUM: Number of patients who underwent induction treatment as CT or CT+RT in the 6 months prior to surgery;            DEN: Total number of surgical patients;            The algorithm will not be able to identify patients who received neoadjuvant therapy in clinical trials.            For major surgery, ICD-9-CM codes were selected as reported for KPI 3.
														
6	
30-day mortality rate from major surgery            NUM : Number of patients who died within 30 days from major surgery;            DEN: Total number of surgical patients;            For major surgery, ICD-9-CM codes were selected as reported for KPI 3.
														
7	
Percentage of patients discussed in the multidisciplinary team (MDT) meeting at least once in the year of incidence            NUM: Number of patients discussed at least one time in MDT meetings;            DEN: Total number of patients identified by the algorithm;
														
8	
Percentage of patients who performed imaging exams such as MRI, TC and PET within 7 days from MDT meeting            NUM: Number of patients who performed imaging exams within 7 days from MDT meeting;            DEN : Total number of patients discussed in MDT meeting;
														
9	
Average and range of length of stay calculated as the mean difference among date of discharge and date of admission.
														
10	
Average time between biopsy and the first administration of systematic anti-cancer drug (excluded neoadjuvant patients of KPI 5) calculated as the average difference among biopsy and the first date of administration of chemotherapy.            For patients enrolled in experimental clinical trial will not be possible to retrieve information on therapies from administrative database.
														

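### KPI 3 and the KPI 5 anchor date are worded as major lung resection, but the code list behind them includes a pleural procedure (34.6)

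*Protocol*

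**What the plan says.** Protocol 5.2 titles KPI 3 "Percentage of major surgical resections within the year of analysis" and defines its numerator as "Number of patients who underwent to lung cancer major surgical resection". The denominator is every patient whom the algorithm identifies.

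The KPI 5 title counts chemotherapy, with or without radiotherapy, "within 6 months prior to the first major resection date". Section 5.1 lists the matching variable as "Neoadjuvant treatment before lung cancer surgical resection".

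Only one code table puts these terms into practice. It is introduced by "To identify major surgical procedures for lung, the following codes of ICD-9-CM classification will be identified" and headed "ICD-9-CM coding related to major surgery on lung". Its six codes are 32.01 ("ENDOSCOPIC EXCISION OR DESTRUCTION OF LESION OR TISSUE OF BRONCHUS"), 32.29, 32.3, 32.4, 32.5 and 34.6 ("SCARIFICATION OF PLEURA"). KPIs 4, 5 and 6 take their major-surgery codes from the same table. KPIs 10 and 11a exclude the patients whom KPI 5 classes as neoadjuvant. The protocol nowhere limits KPI 3 or KPI 5 to part of the table, and it does not explain why 34.6 is there.

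**The concern.** The label and the codes describe different things. The printed label of 34.6 names the pleura and no removal of tissue. It does not fit the resection wording of KPI 3 and the KPI 5 title, nor the table's own heading, which refers to the lung.

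KPI 3 serves the primary objective. If 34.6-only patients exist, a figure presented as a resection rate includes people with no resection. That error is systematic, so the confidence interval does not reflect it. The planned validation (4.2) compares only NSCLC with non-NSCLC status and would not reveal it.

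KPI 5 depends on a date. If a pleural procedure sets that date, the six-month look-back is measured from the wrong event. Section 3 describes a cohort in which every patient received an anti-cancer drug in 2017 (4.1 does not repeat this). On that reading, the KPI 5 class of a 34.6-only patient depends on the type of drug and on the order and interval of drug and procedure.

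**Working it through.** **Inputs.** N is about 400 (7.2). The share advanced at diagnosis is 79% (Section 1). The protocol gives no expected value for any KPI and no formal sample size calculation, so there is no figure of its own to reproduce. Every patient count below other than N is an assumption.

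**KPI 3.** Let R be the patients with at least one listed code other than 34.6, and x those whose only listed code is 34.6. Each patient counts once and the denominator does not depend on the table:

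- as written: (R + x)/N
- without 34.6: R/N
- difference: x/N, which is zero or positive

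| N | x = 0 | x = 4 | x = 10 | x = 20 |
|---|---|---|---|---|
| 350 | 0 | 1.1 | 2.9 | 5.7 |
| 400 | 0 | 1.0 | 2.5 | 5.0 |
| 450 | 0 | 0.9 | 2.2 | 4.4 |

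(percentage points)

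For scale, 0.79 × 400 = 316 advanced patients, leaving 84. If R = 84, KPI 3 is 84/400 = 21.0% (exact 95% CI 17.1 to 25.3%). With x = 4, 10 or 20 it becomes 88/400 = 22.0%, 94/400 = 23.5% or 104/400 = 26.0%. Only the last lies outside the interval.

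**KPI 5, direction.** Six months is taken as 183 days, with one chemotherapy date per patient.

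- Chemotherapy day 0, 34.6 on day 60, no resection: classed as neoadjuvant, although nothing was resected.
- Chemotherapy day 0, 34.6 on day 100, lobectomy (32.4) on day 240: classed as neoadjuvant because 100 is within 183. Measured from the lobectomy, 240 is outside the window.
- 34.6 on day 0, chemotherapy day 20, lobectomy on day 110: not classed as neoadjuvant, because the anchor is day 0. Measured from the lobectomy, chemotherapy came 90 days before and qualifies.
- 34.6 on the same day as the resection, or after it: no change.

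Both kinds of error are therefore possible.

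**KPI 5, size.** KPI 5 = (T + k − j)/D, where T is the number of true neoadjuvant patients, k those wrongly added, j those missed, and D = R + x + E, with E the exploratory-only patients. With R = 84, x from 4 to 20 and E from 0 to 20, D runs from 88 to 124. One misclassified patient moves KPI 5 by 1/88 = 1.1 to 1/124 = 0.8 points. Example with T = 12, x = 10, E = 10 (D = 104): 12/104 = 11.5% with no errors, 17/104 = 16.3% with k = 5, and 10/104 = 9.6% with j = 2.

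**KPIs 4 and 6.** The 34.6-only patients also enter the count of surgical patients. In KPI 4, an assumed 10 exploratory-only patients give 10/94 = 10.6% without them and 10/104 = 9.6% with x = 10. In KPI 6 they enter the denominator, and any of them who die within 30 days also enter the numerator, so the direction is open.

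**The case against.** The best defence is that the panel meant surgery and used resection loosely. The table's introduction and heading both speak of surgery, and the KPI 5 numerator and denominator refer to surgery and surgical patients. This stands in part: the documents do not settle whether the label or the list is wrong. But 34.6 does not fit the heading either, since its label is pleural, so a loose label does not explain it. The table is also marked as a draft and the indicators as potential. That leaves room to correct the list but does not correct it.

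A reader might infer more in four respects.

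- **That 32.01 is equally wrong.** Its label shares the words for excision or destruction of a lesion or tissue with 32.29, and bronchial tumours belong to the disease definition in 4.1. Whether an endoscopic excision is major is a coding judgement that the protocol does not settle.
- **That the resection rate is materially inflated.** No count of 34.6-only patients is given, and zero is possible. The base of 84 applies a background figure to a drug-treated cohort and assumes that every remaining patient was resected.
- **That the immunotherapy indicator is compromised.** KPI 11a is touched only through the KPI 5 exclusion. The direction is unknown and the effect probably small.
- **That the list is sound wherever the wording is surgery.** KPIs 4 and 6 reuse the same lung-surgery table, so the question about 34.6 applies there too.

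**Conclusion.** The point holds for 34.6. As written, KPI 3 counts a 34.6-only patient as resected, and 34.6 can set the KPI 5 anchor date. The effect on KPI 3 is exactly x/N and never negative. KPI 5 can move either way, by about 0.8 to 1.1 points per misclassified patient under the assumed denominators. The mismatch and the directions follow from the protocol's text alone; the sizes rest on assumed counts, with ranges that start at zero. For 32.01 the documents support a query only. This is an inconsistency to settle before the analysis is run, in a descriptive study without hypothesis tests. It is not evidence that the results will be far off.

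**What to change.** Reconcile the label and the list before analysis, in one of two ways:

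1. Remove 34.6 from the codes used for the KPI 3 numerator and the KPI 5 anchor date, derive the KPI 10 and 11a exclusions from that date, and report the number of 34.6-only patients separately so that x is visible.
2. If the broader concept is intended, rename KPI 3 and the KPI 5 anchor accordingly and also report the resection-only figure.

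Apply the same decision to KPIs 4 and 6 and to the surgical-patient denominator of KPI 5. Ask the expert panel to confirm whether 32.01 counts as major resection, and show KPI 3 with and without it.

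The cost is one table edit and a rerun of the query. If fewer patients count as surgical, intervals widen slightly. With an assumed 12 neoadjuvant patients, the exact 95% CI is 5.6 to 17.7% for 114 surgical patients (84 + 20 + 10) and 6.8 to 21.2% for 94 (84 + 10). Under the first option the main figure no longer covers the panel's whole list, but the separate count keeps that information.

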### **7.3 Data analysis**

For primary objective, for each indicator, the proportion of patients who receive the procedure, in the defined time window, among those eligible will be calculated. Descriptive statistics as arithmetic mean and standard deviation (SD) as well as median value and minimum–maximum statistics will be presented for KPI related to average time. Two-sided 95% confidence interval (95% CI) will be reported as appropriate and specified for KPI expressed as proportion. For secondary objective, the validity of algorithm will be evaluated by individual matching among cases retrieved from administrative database and medical chart obtained from IRST. Following definition will be used to explain this objective: NSCLC cases appearing as incident cases in administrative database, but not in IRST clinical chart will be considered as false positive and those appearing in IRST clinical chart but not in administrative database will be considered as false negatives.

Sensitivity will be defined as the percentage of NSCLC cases correctly identified by the algorithm and calculated as the proportion among NSCLC cases identified both in administrative database and IRST clinical chart ('true positive' cases) and all cases identified as NSCLC cases from IRST clinical chart ('true positive' + 'false negative' cases). Positive predictive value will be defined as the percentage of NSCLC patients identified from IRST clinical chart were really NSCLC. This proportion will be calculated as the proportion among NSCLC cases identified both in administrative database and IRST clinical chart ('true positive' cases) and all cases identified as NSCLC cases from administrative database ('true positive' + 'false positive' cases).

Likewise, specificity and negative predictive value will be calculated, and exact (Clopper-Pearson) 95% confidence limits for binomial distribution will be applied.

Statistical analysis will be performed using Stata software 15.1/SE for Windows (Stata Corp LP, USA).

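### KPI 6 counts deaths after major surgery but divides by all surgical patients, a term the protocol defines to include exploratory-only patients; KPI 5's numerator and denominator need reconciling with its heading

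*Protocol*

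**What the plan says.** All the indicator definitions are in the table in Protocol section 5.2.

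- **KPI 3** lists the ICD-9-CM codes that count as major lung surgery. Code 34.02 (exploratory thoracotomy) is not among them.
- **KPI 4** takes patients whose only procedure was an exploratory thoracotomy (34.02) as numerator and surgical patients as denominator. Its row closes with the protocol's only definition of that denominator: "Surgical patients defined as patients who receive any surgical procedure (major and/or explorative".
- **KPI 5** (neoadjuvant therapy) has a heading that sets the window "within 6 months prior to the first major resection date". Its numerator is "Number of patients who underwent induction treatment as CT or CT+RT in the 6 months prior to surgery" and its denominator "Total number of surgical patients". Section 5.1 lists the matching variable as "Neoadjuvant treatment before lung cancer surgical resection".
- **KPI 6** is headed "30-day mortality rate from major surgery". Its numerator is "Number of patients who died within 30 days from major surgery" and its denominator again "Total number of surgical patients".

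The rows for KPIs 4, 5 and 6 all carry the same note, that major surgery is identified by the KPI 3 codes. Section 7.3 gives the general rule for proportions: patients who receive the procedure "in the defined time window, among those eligible will be calculated".

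**The concern.** KPI 6 has a numerator and a denominator on different populations. A patient who had only an exploratory thoracotomy has no major-surgery date, so cannot die within 30 days of one, yet is counted among surgical patients under the KPI 4 definition. Every such patient lowers the reported rate, so the error can only make mortality look better.

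KPI 6 serves the primary objective (section 2.1), which concerns appropriateness and quality of care at the participating sites. As written, it would depend on how often a site ends an operation at exploration, which is what KPI 4 measures. It would no longer reflect mortality after major surgery alone.

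KPI 5 raises a different question. Its numerator and denominator are both worded for surgery in general, while its heading and section 5.1 concern resection. This also matters downstream, because KPIs 10 and 11a exclude the neoadjuvant patients of KPI 5.

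**Working it through.** The protocol states no surgical, exploratory or mortality rate, and section 7.2 says no formal sample size calculation was made. There is no figure to reproduce, and every rate below is an assumption.

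**KPI 6, algebra.** Let M be patients with a KPI 3 major-surgery code, E exploratory-only patients, d deaths within 30 days of major surgery, and s = E/(M+E). Then

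- rate named in the heading: d/M
- rate as written, with the KPI 4 definition: d/(M+E) = (d/M) × (1 − s)

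The relative understatement is exactly s, which is also KPI 4 as its numerator and denominator are written.

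| Assumed d/M | s = 5% | s = 10% | s = 20% |
|---|---|---|---|
| 1.0% | 0.95% | 0.90% | 0.80% |
| 3.0% | 2.85% | 2.70% | 2.40% |
| 5.0% | 4.75% | 4.50% | 4.00% |

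Two sites that both have 3.0%, with s = 5% and s = 20%, would report 2.85% and 2.40%, an artificial gap of 0.45 points.

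**KPI 6 against sampling error.** For a rough scale, take the cohort of about 400 (section 7.2) and the background figure of 79% advanced at diagnosis (section 1): 400 × (1 − 0.79) = 84. Assume that all 84 had major surgery and 3 died within 30 days. Exact (Clopper-Pearson) 95% intervals:

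| Exploratory-only added | s | KPI 6 | 95% CI |
|---|---|---|---|
| 0 | 0% | 3/84 = 3.57% | 0.74 to 10.08% |
| 4 | 4.5% | 3/88 = 3.41% | 0.71 to 9.64% |
| 9 | 9.7% | 3/93 = 3.23% | 0.67 to 9.14% |
| 21 | 20% | 3/105 = 2.86% | 0.59 to 8.12% |

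The largest shift is 3.57 − 2.86 = 0.71 points, inside an interval more than 9 points wide.

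**Recovery.** Since KPI 4 = s, d/M = KPI 6/(1 − KPI 4). For example, 2.40%/(1 − 0.20) = 3.00%.

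**KPI 5, side by side.**

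| Element | Anchor |
|---|---|
| Heading | first major resection |
| Section 5.1 variable | surgical resection |
| Numerator | surgery, unqualified |
| Denominator | surgical patients (by the KPI 4 definition, major or exploratory) |

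The last two rows match each other and conflict with the first two. No shrinkage factor follows from the literal wording.

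**The case against.** **The definition may be local to KPI 4.** It closes the row in which exploratory patients are the subject, and KPIs 5 and 6 do not repeat it. KPI 6's heading, numerator and code note all speak of major surgery, and section 7.3 can be used to resolve the ambiguity in favour of a major-surgery denominator. This is a reasonable guess at the intent, and it makes it too strong to say that KPI 6 has no usable denominator. But the protocol never states it. The code note does not settle the matter, because the same note stands under KPI 4, where exploratory patients are expressly included.

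**The effect is small and reversible.** This stands. All rates are assumed, the study is descriptive with no hypothesis test, and the correction is available from KPI 4 if both are reported by site. Section 7.3 specifies no between-site comparison, so the 0.45-point gap bears only on an informal reading of site values. If the 84 patients split evenly over three sites (28 each), one death gives 1/28 = 3.6%, with an exact 95% interval of 0.1 to 18.3%. A gap of 0.45 points would not be visible.

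**The rough scale may not fit the cohort.** This also stands. Section 3 describes patients with at least one anti-cancer drug treatment in 2017, a condition that section 4.1 does not repeat. If it applies, patients who die soon after upfront surgery without drug treatment never enter. Neither the 84 nor the assumed mortality then follows, and the corrected denominator would describe only the drug-treated cohort.

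**KPI 5 might be thought to shrink by the same factor.** A reader might infer that an assumed 20% would read 19.0%, 18.0% or 16.0% at shares of 5%, 10% or 20%. That needs the numerator to be read as major resection while the denominator one line below is read literally. The document does not support mixing the two readings. Taken literally, both refer to surgery in general; taken by the heading, both should refer to major resection.

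**Conclusion.** For KPI 6 the point holds as written: under the protocol's only definition of surgical patients, 30-day mortality after major surgery is understated by a relative amount equal to the exploratory-only share, contrary to the eligibility rule in section 7.3. The direction is certain if that definition is applied and any exploratory-only patients exist. The size is unknown and probably small: 0.15 to 0.60 points at an assumed 3.0% mortality and shares of 5% to 20%. That is within sampling error and changes no test.

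For KPI 5 the finding is narrower. Its numerator and denominator agree with each other but conflict with its heading and section 5.1, which leaves open who counts as a neoadjuvant patient and so who is removed from KPIs 10 and 11a. A numerical bias in KPI 5 is not shown.

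**What to change.** - **KPI 6:** state the denominator as patients with at least one KPI 3 major-surgery code.
- **KPI 4:** keep the broad definition of surgical patients here and say that it applies to this indicator only.
- **KPI 5:** anchor both numerator and denominator on the first KPI 3 major resection, in line with the heading and section 5.1. State that the exclusions in KPIs 10 and 11a use this group.

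The cost is wording only, made before the indicators are programmed. The data and code list are already in the protocol. If exploratory-only patients exist, reported KPI 6 mortality will be slightly higher than under the broad definition.

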## **3. STUDY DESIGN**

This is a multi-center, observational study involving retrospective collection of NSCLC patients information. All consecutive patients who had a newly diagnosis of NSCLC in 2017 from healthcare administrative database and received at least one anti-cancer drug treatment between January 2017 and December 2017, identified through the proposed algorithm, will be considered. All data needed for KPI calculation, even if they fall outside January-December 2017 period, will be collected. The end of data collection will be defined as patient death or 30 June 2018, whichever came first.

A set of potential KPIs had been developed from a panel of experts (clinicians, IT experts etc..) to investigate the appropriateness of activities within NSCLC care pathway, with a special focus on the use of immunotherapy.

The eligible population and data will be gathered retrospectively through an algorithm from administrative databases (SDO, REM, ASA, FED, AFT, ADI, SDHS-hospice).

Administrative data will be used as unique resource:

- to identify patients cohort;
- to measure KPIs along care pathway ;

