11	
KPIs on THERAPIES For patients enrolled in experimental clinical trial will not be possible to retrieve information on therapies from administrative database.
 
a) Percentage of patients treated with immunotherapies NUM: Patients with at least one administration of immunotherapy According to Anatomical Therapeutic Chemical Classification System ATC, the following codes will be investigated: L01XC17 nivolumab L01XC18 pembrolizumab L01XC32 atezolizumab
 
DEN: Total number of patients identified by the algorithm who underwent anti-cancer drug treatment for NSCLC, as single or double agent chemotherapy, target therapy etc..(excluded neoadjuvant patients of KPI 5)
 
b) Percentage of patients who underwent immunotherapy for more than 6 months after first dose. NUM: Number of patients who underwent immunotherapy more than 6 months after the first administration; DEN: Total number of patients identified by the algorithm who underwent immunotherapy;

12	
Percentage of patients who underwent anti-cancer drug treatment in the last 30 days of life NUM: Number of patients who underwent anti-cancer drug treatment in the last 30 days of life; DEN: Total number of patients identified by the algorithm who deceased

13	
Percentage of patients who underwent the first administration of systematic anti-cancer drug within 30 days from discussed in MDT meeting NUM: Number of patients who underwent first systematic anti-cancer drug administration within 30 days from MDT; DEN: Total number of patients patients identified by the algorithm discussed in MDT meeting;

14	
Percentage of patients who underwent RT in the last 30 days of life ( excluded palliative treatments single fraction) NUM: Number of patients who performed RT in the last 30 days of life ( excluded palliative treatments); DEN: Total number of patients identified by the algorithm who deceased;

15	
Percentage of patients who underwent at least one Integrated Home Care (IHC) NUM: Number of patients who underwent IHC service; DEN: Total number of patients identified by the algorithm;

16	
Percentage of patients who underwent at least one hospice care NUM: Number of patients who underwent hospice care; DEN: Total number of patients identified by the algorithm;

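### KPIs 10 and 11a exclude patients given drugs before resection but keep those first treated after it, so the resection share affects time to first drug and, less strongly, the immunotherapy percentage

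*Protocol*

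**What the plan says.** Protocol section 5.2 defines both indicators.

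- KPI 10 is "Average time between biopsy and the first administration of systematic anti-cancer drug". Its only exclusion by treatment pathway is "excluded neoadjuvant patients of KPI 5".
- KPI 11a has the numerator "Patients with at least one administration of immunotherapy" (nivolumab, pembrolizumab or atezolizumab). Its denominator is "Total number of patients identified by the algorithm who underwent anti-cancer drug treatment for NSCLC, as single or double agent chemotherapy, target therapy etc", less the same KPI 5 patients.
- KPI 5 fixes who is removed: "Number of patients who underwent induction treatment as CT or CT+RT in the 6 months prior to surgery". Drug treatment after surgery is not covered.

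Section 3 takes new 2017 diagnoses who "received at least one anti-cancer drug treatment between January 2017 and December 2017", with no limit on stage or treatment intent. Resected patients belong to this cohort, since KPI 3 counts the "Number of patients who underwent to lung cancer major surgical resection" among all patients the algorithm finds. No section mentions adjuvant treatment, or separates patients whose first drug came after resection. Section 7.3 gives mean, SD, median and range for time indicators, and proportions with 95% confidence intervals where appropriate. Section 2.1 states the purpose: appropriateness and quality of care among the participating sites.

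**The concern.** Both indicators set aside drug treatment linked to surgery, but only when it comes before the operation. A patient who is biopsied, resected and then given a first drug stays in KPI 10. Part of that patient's interval is recovery from surgery, which is not delay in starting drug treatment. The same patient sits in the KPI 11a denominator through post-surgical chemotherapy, while section 1 describes immunotherapy as an option in advanced disease.

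The indicators are meant to describe quality of care across three sites, and resection share is a feature of case mix that may differ between them. A difference in KPI 10 or KPI 11a could then be read as a difference in promptness or in uptake of immunotherapy when it reflects only how many patients were operated on.

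**Working it through.** The protocol states no figure to reproduce. The 400 patients in section 7.2 are a feasibility count, and no formal sample size calculation was made. The check is a reading of the definitions, followed by a mixture calculation on assumed inputs.

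**Do these patients enter both indicators?** Yes. They have a drug record and no induction treatment, so KPI 5 does not remove them. KPI 10 needs a biopsy date and a first-drug date; KPI 11a needs any anti-cancer drug.

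**Inputs, all assumed because the documents give none of them**

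- *a*, share of the indicator's patients first treated after resection: 10-20%. Section 1 puts 79% at an advanced stage at diagnosis, leaving 21% not advanced. That is a rough anchor and not a bound among drug-treated patients.
- *D*, extra days from biopsy to first drug in those patients: 50-70.
- *p*, immunotherapy share in the other patients: 30%.
- *r*, immunotherapy share in patients first treated after resection: taken as 0, the extreme case.

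**KPI 10.** Rise in the mean = *a* × *D*.

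- Low end: 0.10 × 50 = 5 days.
- High end: 0.20 × 70 = 14 days.

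**KPI 11a.** Reported share = *p*(1 − *a*) + *r* × *a*. With *r* = 0 the drop is *p* × *a*, its largest value.

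- *a* = 10%: 0.30 × 0.90 = 27%.
- *a* = 20%: 0.30 × 0.80 = 24%.

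Section 3 collects data to death or 30 June 2018, so patients who relapse and receive immunotherapy by then make *r* greater than 0 and the drop smaller.

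**Two sites with identical practice.** Assume a mean of 30 days without prior resection and 90 days with it, so *D* = 60, and *a* of 10% at one site and 20% at the other.

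| | Site with *a* = 10% | Site with *a* = 20% |
|---|---|---|
| KPI 10 mean | 30 + 0.10 × 60 = 36 days | 30 + 0.20 × 60 = 42 days |
| KPI 11a (*r* = 0) | 27% | 24% |

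**Scale against sampling error.** With all 400 patients in the KPI 11a denominator, the 95% half-width at 27% is 1.96 × √(0.27 × 0.73 / 400) = 4.35 points. A shift of 3 points is smaller than that even for the pooled cohort, and single-site intervals are wider.

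**The case against.** **KPI 11a may be meant broadly.** Its denominator names chemotherapy and targeted therapy as well, so it reads as a utilisation share among drug-treated patients. This stands. A reader might infer that KPI 11a is wrong because post-surgical patients dilute it. The documents do not support that: section 1 places immunotherapy in advanced disease as background and does not make eligibility the denominator. What remains is that removing only the pre-surgical group is unexplained and leaves the percentage sensitive to the resection share.

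**The full surgical pathway is not always inside the KPI 10 interval.** If tissue is first obtained at the operation, the wait for surgery is not counted. This also stands, although recovery is still included.

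**Excluding these patients could do harm.** A reader might infer that they should be dropped as the neoadjuvant patients are. The KPI 3 code list includes 34.6 (scarification of pleura) and 32.01 (endoscopic procedure on the bronchus), and neither shows a lung resection by itself. Exclusion on that list could remove unresected patients with advanced disease. It would also remove patients who were resected, relapsed and received immunotherapy as their first drug. This defeats exclusion but not separate reporting.

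**A reader has other clues.** The study is descriptive, KPIs 2 and 3 show the metastatic and resected shares, and the median accompanies the mean. These warn of case mix but do not separate the two pathways, and KPI 11a has no median.

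**The analysis plan could add strata.** It could, but the numerators, denominators and exclusions are already fixed in section 5.2, and the one-sided exclusion is part of them.

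**Conclusion.** The point holds mainly for KPI 10. As written, it averages time to primary drug treatment together with an interval that includes recovery from surgery and often the surgical wait and operation. Under the assumed 10-20% share and 50-70 extra days, the mean rises by 5-14 days. KPI 11a remains a valid share of all drug-treated patients but moves with the resection share. The drop is at most *p* × *a*, so an assumed 30% reads no lower than 27% to 24%.

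The asymmetry is in the definitions and does not depend on these figures. Its size does, and cannot be taken from the documents. The figures should therefore not be quoted as the bias that will occur. The change is a cheap improvement to the interpretation of site figures, and its absence does not invalidate either indicator.

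**What to change.** Keep the overall KPI 10 and KPI 11a as defined. In addition, report KPI 10 as the priority, and KPI 11a alongside it, separately for patients with and without a lung resection dated before the first recorded drug. Define that flag from the resection codes in the KPI 3 list (32.29, 32.3, 32.4, 32.5) and not from 34.6 or 32.01. Do not exclude these patients outright.

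Resection and drug dates are already needed for KPI 5, so the work is one date comparison. The cost is a line or two more per indicator and smaller strata. At an assumed 10-20% of at most 400 patients, the prior-resection stratum would hold at most 40 to 80 patients over three sites (400 × 0.10 and 400 × 0.20), so its site-level figures would be imprecise.
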